Those who meet the inclusion criteria will be invited to participate in this study. Eligible participants shall meet all the following inclusion criteria.

- 1) Newly diagnosed prediabetic individuals who have been first seen by clinical dietitian registered under the Ministry of Health Malaysia.
- 2) Malaysian ≥ 18 years old.
- 3) Those who plan to continue prediabetes care at a community clinic in Melaka.
- 4) Those who can read, write and understand the Malay Language.

Participants who meet the following criteria will be excluded from continuing the study.

- 1) Night shift workers at least 3 times per week.
- 2) Known sleep disorder.
- 3) Pregnant Women.
- 4) Those on oral glucose-lowering medications, diabetes supplements, anticonvulsant medications or oral steroids currently or in the last month.
- 5) Those with prior explored to any information regarding time-of-eating/time-of-activity restriction.
- 6) Those with chronic kidney disease. They are excluded as current research lack of evidence to support the accuracy of using 24-hour continuous glucose monitoring system (CGMS) (Freestyle Libre Pro, Abbott, Germany).

Prediabetes and diabetes will be defined according to the latest Clinical Practice Guideline in Malaysia (WHO & IDF, 2006; ADA, 2020; MOH *et al.*, 2020). Diagnosis must be confirmed by measurement of venous plasma glucose (FBG and OGTT) or HbA1c level. Table 1 shows the diagnostic value for diabetes on plasma glucose. Table 2 shows the diagnostic values for prediabetes and diabetes based on OGTT. Table 3 shows the diagnostic values for prediabetes and diabetes based on HbA1c. All the tables are adapted from the Clinical Practice Guideline in Malaysia (WHO & IDF, 2006; ADA, 2020; MOH *et al.*, 2020).

Table 1 The diagnostic value for diabetes on plasma glucose

	Fasting	Random
Venous Plasma Glucose	≥ 7.0 mmol/L	≥ 11.1 mmol/L

In symptomatic individual, one abnormal glucose value is diagnostic.

In asymptomatic individual, 2 abnormal glucose value are required.

Table 2 The diagnostic values for prediabetes and diabetes based on OGTT

OGTT Plasma Glucose Values (mmol/L)		
Category	0 hour	2- hour
Normal	<6.1	<7.8
IFG	6.1-6.9	
IGT	-	7.8-11.0
DM	≥ 7.0	≥ 11.1

IFG= impaired fasting glucose; IGT=impaired glucose tolerance; DM=diabetes mellitus

Table 3 The diagnostic values for prediabetes and diabetes based on HbA1c

	Normal	Pre-diabetes	Diabetes
A1c	<5.6% (38mmol/mol)	5.6-6.2% (38-44 mmol/mol)	≥6.3% (45mmol/mol)

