research assistant using the following questionnaire including (1) Munich Chronotype Questionnaires (MCTQ) (Appendix D), (2) Pittsburgh Sleep Quality Index Questionnaire (PSQI) (Appendix H), (3) Harvard Light Exposure Questionnaire (HLEQ) (Appendix G), (4) International Physical Activity Questionnaire (IPAQ) (Appendix C) and (5) Chrononutrition Profile Questionnaire (CPQ) (Appendix I). Anthropometry measurements including body fat, height, body fat percentage, visceral fat, waist circumference and hip circumference will be measured. Participants are requested to fill up 3-days dietary record (3DDR) (2 weekdays and one weekend day) and the data will be collected in the next visit. Baseline reading of fasting plasma glucose (FPG, OGTT, liver function, and HbA1c) will be retrieved from medical records in the community clinic. Routine treatment will be provided as usual. To minimize the loss of follow-up, phone conversations will be made to ensure the 3-days dietary data is completed.

At the second visit (three months from the baseline), all participants are required to wear a CGMS sensor at the back of their upper arms to measure the 24 hours glucose fluctuation over 14 consecutive days. 3DDR will be given to participants to record their consecutive 3 days dietary record and will be returned after 14 days. After 14 days, participants will return the CGMS sensor at the community clinic. Or alternative way of CGMS sensor collection by an assistant at the participant's home. All questionnaires will be interviewed by a trained research assistant again. Anthropometry measurements including body fat, height, body fat percentage, visceral fat, waist circumference and hip circumference will be measured repeatedly.

At the third visit (six months from the first visit), for FBG, OGTT and HbA1c test, all the readings will be retrieved by the research assistant from the medical record to document the glycemic outcome. The participants will be interviewed by the trained research assistant during all clinic visits using similar questionnaires. All anthropometry measurements (body fat, height, body fat percentage, visceral fat, waist circumference and hip circumference) will be conducted again. 3DDR will be given to record their 3 days dietary intake again and the record progress will be followed up through phone. The original 3DDR will be collected at the routine appointment.

Sample size Calculation:

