The sample size is estimated using G*Power software version 3.1.9.4 (Erdfelder, Faul and Buchner, 1996). To determination of association between chrononutrition and glycemic control, the β -coefficient of 0.13 adopted from Sakai *et al.*, (2018), the power was set to 0.9 with 2 sided significance level and alpha error given 0.05, a total of 83 prediabetic adults expected in this study. To compensate for the non-responding and non-compliance during follow-up, a dropout rate of 50% will be considered, the total sample size required is 166 subjects in the study for 6 months.

Test Family: T Test

Statistical Test: Linear Multiple Regression Fixed Model, single regression coefficient

Tail(s): 2

Effect Size (β -coefficient): 0.13 (Sakai *et al.*, 2018)

α Error prob: 0.05

Power(1- β err prob): 0.90

[figure not shown]
Total Sample Size: 83 prediabetes individuals

50% dropout rate taken as consideration in study for 6 months follow up, total 166 prediabetes individuals shall be recruit in this study.

Dropout Rate:

$$= \frac{83}{1-0.5} = 166 \text{ prediabetic individuals}$$

Figure 3: Flow diagram of the study design

Participants will be undergoing OGTT, FBS and HbA1c tests after an overnight fast of 8-10 hours. This is a routine universal test for prediabetes/ diabetes diagnosis. Participants will be informed to eat their usual diet for three days prior to the test. The diagnostic value for diabetes on plasma glucose. the diagnostic values for prediabetes and diabetes based on OGTT, and the diagnostic values for prediabetes and diabetes based on HbA1c have been shown in Table 1, Table 2 and Table 3, respectively. Fasting blood sample will be taken for FBS and HbA1c tests. Subsequently, participants will be given 75-gram glucose water to drink within 5 minutes. Blood sample will be taken after 2 hours for glucose determination. Participants should rest throughout test with only plain water is allowed to drink. Figure 4 shows the procedure of OGTT. All the tests will be conducted in the healthcare clinic lab. Results will be traced from medical record.

Table 4: Summary of data collection and timeline

Data	Baseline	3 months	6 months
Sociodemographic			
Age	.	.	.
Date of Birth	.	.	.
Marital Status	.	.	.
Education Level	.	.	.
Occupation	.	.	.
Monthly Household Income	.	.	.
Health History	.	.	.
Smoking Habit	.	.	.
Supplementary Consumption	.	.	.
Anthropometry			
Weight	.	.	.
Height	.	.	.
Waist Circumference	.	.	.
Visceral Fat	.	.	.
Body Fat	.	.	.

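### The plan expects 50% loss and, in the sample size and analysis, answers it only by inflating 83 to 166. It gives no missing-data method and no commitment to obtain the six-month clinic-record outcomes of people who stop study procedures.

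*Combined protocol and SAP*

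**What the plan says.** Section 3, Sample size Calculation, arrives at "Total Sample Size: 83 prediabetes individuals" and then allows for loss: "To compensate for the non-responding and non-compliance during follow-up, a dropout rate of 50% will be considered". The dropout formula there is 83/(1 − 0.5) = 166.

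The Statistical Analysis text names generalized linear models, ANCOVA and logistic regression. It defines no analysis set and gives no method for missing data, no comparison of completers with dropouts, and no sensitivity analysis. Data monitoring and management only has entered data checked for outliers and missing values.

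The account of the third visit, at six months, says of fasting glucose, OGTT and HbA1c that "all the readings will be retrieved by the research assistant from the medical record to document the glycemic outcome". Section 1 describes a second OGTT within six months as part of routine care, and section 3 calls these tests routine and has them run in the clinic laboratory. Inclusion criterion 3 admits "Those who plan to continue prediabetes care at a community clinic in Melaka". The fourth main outcome, CGM, comes from a study sensor. Meal timing, chronotype and most covariates come from interviews and diaries.

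Two retention measures appear in section 3: phone calls to see that the diet record is completed, and collection of the sensor at the participant's home.

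**The concern.** The stated causes of loss are non-response and non-compliance with follow-up. People who do not complete diaries and visits may differ from those who do in when they eat and in their glycaemia, which are the exposure and outcome under study. If so, the 83 who remain are a selected half, and the estimated association can be too small or too large. Enrolling twice as many people makes that estimate more precise without making it less selected.

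Three of the four main outcomes do not depend on a diary, questionnaire or sensor. Someone who stops study procedures but attends the routine six-month clinic test still has a fasting glucose, a 2-hour glucose and an HbA1c on file. The plan does not say that these will be sought, so part of the planned loss may be avoidable.

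**Working it through.** **1. The plan's own figures.** Inputs from the Sample size Calculation: "α Error prob: 0.05", two tails, "Power(1- β err prob): 0.90", "Effect Size (β -coefficient): 0.13" and "Statistical Test: Linear Multiple Regression Fixed Model, single regression coefficient". Power comes from the noncentral t distribution with noncentrality √(f²·N) and N − p − 1 degrees of freedom. With 0.13 entered as f², N = 83 for p = 1, 2, 5 or 6 predictors, and power at 83 is 0.901. Inflation gives 83/(1 − 0.5) = 166. Both figures reproduce, so the arithmetic is sound. (If the 120 in the synopsis is what is enrolled, 50% loss leaves 60 and power falls to 78.4%.)

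**2. What selective loss does to the slope.** The documents give no reason for dropout, so its strength is an assumption. Exposure and outcome are standard normal with correlation r, and dropout is logistic and averages 50%. Two values of r bound the range:

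- r = 0.13, if the stated coefficient is read as standardised;
- r = √(0.13/1.13) = 0.34, which f² = 0.13 implies.

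The table gives the completers' slope divided by the true slope. Simulation error is about 0.01 at the lower correlation.

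| Dropout depends on | Log-odds per SD | Ratio, r = 0.13 to 0.34 |
|---|---|---|
| exposure alone | 0.7 | 1.00 |
| outcome alone | 0.7 | 0.90 to 0.91 |
| both, same direction | 0.7 each | 0.22 to 0.69 |
| both, opposite directions | 0.7 each | 1.62 to 1.17 |
| both, same direction | 0.35 each | 0.77 to 0.90 |
| both, opposite directions | 0.35 each | 1.19 to 1.05 |

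In absolute terms, the same-direction case at 0.7 shifts the standardised slope by (1 − 0.22) × 0.13 = 0.10 or (1 − 0.69) × 0.34 = 0.11. The standard error at 83 is roughly 1/√83 = 0.11, so this bias is about one standard error.

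**3. What it does to a mean change.** The completers' mean differs from the cohort mean by the lost fraction times the completer–dropout difference. For an assumed difference of 0.3 SD, that is 0.5 × 0.3 = 0.15 SD at 50% loss and 0.1 × 0.3 = 0.03 SD at 10% loss.

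**4. What record retrieval could add.** No retrieval rate is given, so the loss is assumed to lie between 5% and 30%. Power uses f² = 0.13, and the standard error relative to 83 participants is √(83/n).

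| Loss of record outcome | n of 166 | Power | SE ratio |
|---|---|---|---|
| 5% | 158 | 99.4% | 0.72 |
| 10% | 149 | 99.2% | 0.75 |
| 20% | 133 | 98.5% | 0.79 |
| 30% | 116 | 97.1% | 0.85 |
| 50% (plan) | 83 | 90.1% | 1.00 |

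With no loss at all the ratio is √(83/166) = 0.71, so a 29% reduction is the upper limit. These figures also assume that the exposure and covariates are available for everyone counted.

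**The case against.** Several points on the other side have force.

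- **The bias is hypothetical.** Nothing in the documents says why people will leave. Loss driven by exposure alone leaves the slope unbiased, and loss driven by outcome alone at log-odds 0.7 costs only about a tenth. Large distortion requires dropout tied to both, and at the correlation implied by the plan's own f² it is milder than at 0.13. This stands, and is why a range is shown.
- **Records are not a complete source.** A reader might infer that six-month outcomes could be had for nearly everyone. The documents do not support that. No retrieval rate is given, and planning to continue care is an intention at entry. Someone who misses the clinic test has no result to retrieve. Use of records after withdrawal depends on consent wording that is not available here.
- **The plan is not wholly passive.** It provides phone calls and home sensor collection, and its statement on retrieving readings is not limited to completers. But the calls concern the diet record, home collection concerns the sensor, and the retrieval statement is written as a step of the third visit. None of these commits to seeking glucose results for people who stop attending study visits.
- **A complete-case analysis is not prescribed.** A reader might infer that the plan defines one. It does not; it is silent. That about 83 completers will be analysed follows from powering on 83 of 166 with no other rule.
- **Records restore outcomes only.** CGM, later meal timing and later covariates stay missing, and energy misreporters are excluded as well. Imputation under missing-at-random does not cure dropout that depends on the unobserved six-month outcome.

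**Conclusion.** The point holds, limited to the sample size and analysis text. A planned 50% loss is met there by inflation alone, with no missing-data method, although three main outcomes come from routine records and could be obtained for more participants than complete study procedures.

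The possible bias runs from none to large and can go in either direction, as tabulated. No single value can be claimed, because the mechanism and strength of dropout are assumed. The gain in precision depends on an unknown retrieval rate: 116 to 158 outcomes out of 166 if 5% to 30% are lost. The benefit is confined to the record-based outcomes, mainly in relation to baseline exposure. This is a worthwhile improvement at low cost, not an error in the stated calculation.

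**What to change.** Add to Statistical Analysis, and to the account of the third visit:

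*Six-month HbA1c, fasting plasma glucose and 2-hour glucose will be retrieved from the clinic record for every enrolled participant who has not withdrawn consent to record use, whatever their completion of visits, diary or CGM. For these three outcomes the main analysis will include all enrolled participants, using multiple imputation from baseline glycaemia, baseline and available 3-month exposures, sociodemographic characteristics and clinic. The complete-case result and a delta-adjusted (missing-not-at-random) analysis will be reported as sensitivity analyses.*

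Also report how many record outcomes were retrieved, and state that CGM and change-in-exposure analyses rest on those who supplied the data. Confirm that the consent wording covers record use after study procedures stop.

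The cost is extra look-ups by the research assistant who already opens these records, one imputation step, and a missing-at-random assumption in the main analysis, which the delta-adjusted analysis is there to test. No visit or test is added.

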Energy and macronutrients analysis of dietary record will be performed using Nutritionist ProTM (Axxya Systems, Stafford, TX, USA), based principally on the Nutrient Composition of Malaysian Food and the food product labels. Energy intake will be compared with estimated basal metabolic rate (BMR) to exclude participants who are under-reporting or overreporting their energy intake in their 3-day food diary. BMR is calculated using standard equations based on sex and age provided by FAO/WHO/UNU (1985) (FAO/WHO/UNU 1985). For participants in a non-dieting population, Torun et al. (1996) proposed that a ratio between energy intake and BMR of less than 1.39 and more than 2.24 be considered as under-reporting and over-reporting respectively. These cut-off points will be applied in the present trial. From the 3-day food diary data, The investigator will investigate the dietary intake as reported on the second day of recording. The second day will be selected over the first one to ensure that participants have also include night-time eating in the records. Compare to the later days, which may have been burdened by increasing exhaustion related to the record-keeping, the second day better represents the habitual dietary intake (Ahola et al. 2019). To investigate the energy and macronutrient intakes over the course of the day, five periods will be performed as follows: night (from 00:00 to 04:49), morning (from 05:00 to 09:59), midday (from 10:00 to 13:59), afternoon (from 14:00 to 16:59) and evening (from 17:00 to 23:59), adapted from Ahola et al. (2019). As these periods differed in their duration, energy intake per hour will also be calculated for each of the five periods. In addition, energy and macronutrient intakes per hour (e.g. intakes reported between 10:00 and 10:59 contributed towards the hour "10:00"). Diet quality will be derived from a 177 food items FFQ at second visit, where the Healthy Eating Index (HEI) will be calculated. This FFQ is adapted from the FFQ used by the Malaysian Adults Nutrition Survey (MANS) 2014 (IPH 2014) (Appendix C). Participants will be required to indicate frequency of foods consumed in the last 1 month. Individual portion size will be asked for each food, and pictures of the various portion size will be

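### The sample size allows for 50% dropout but makes no explicit allowance for the energy-reporting exclusion, so at the planned dropout any such exclusion takes the affected models below 90% power

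*Combined protocol and SAP*

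**What the plan says.** The Sample size Calculation specifies a t test of one coefficient in a multiple regression ("Statistical Test: Linear Multiple Regression Fixed Model, single regression coefficient") and an effect size entered as "Effect Size (β -coefficient): 0.13". From these it concludes: "the power was set to 0.9 with 2 sided significance level and alpha error given 0.05, a total of 83 prediabetic adults expected". It then inflates for attrition: "50% dropout rate taken as consideration in study for 6 months follow up, total 166 prediabetes individuals shall be recruit in this study". The purpose of the 50% is given as "To compensate for the non-responding and non-compliance during follow-up, a dropout rate of 50% will be considered". The site targets under Location of Research (56, 55 and 55) also add up to 166.

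The dietary text under Exposure measures sets a further rule: "Energy intake will be compared with estimated basal metabolic rate (BMR) to exclude participants who are under-reporting or overreporting their energy intake". The limits on the ratio of energy intake to BMR are 1.39 and 2.24, and the text confirms that they apply in this study. It gives no expected proportion outside them. The Statistical Analysis section does not repeat the rule or say which models it affects. The sample size text does not refer to it.

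**The concern.** The number that must be analysed for 90% power and the number expected to remain after dropout are both 83. The plan's own reporting rule can only reduce that number. The rule is worded in terms of participants rather than variables. Read literally, it removes people even from models of HbA1c, fasting glucose and 2-hour glucose whose exposures come from the CPQ or MCTQ and make no use of reported energy.

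At stake is how a null result is read. A reader would judge an absent association between meal timing and glycemia against 90% power, when the analysed set may have supported less. Where the exposure does not depend on diary energy, participants would also be lost without need.

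**Working it through.** **Inputs from the protocol.** Two-sided alpha 0.05; power 0.90; single coefficient in a fixed-model linear regression; effect size 0.13; N = 83; dropout 50%; enrolment 166. No exclusion rate is given, so rates below are assumptions.

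**Step 1: reproduce 83.** Power comes from the noncentral t distribution with δ = √(f² × N) and df = N − p − 1, where p is the number of predictors. With f² = 0.13, N = 83 and p = 1, δ = √10.79 = 3.28, df = 81 and power = 0.901. The smallest N reaching 0.90 is 83, so the plan's figure reproduces when 0.13 is entered as f². The number of predictors hardly matters: power at 83 is 0.9001 with 8 and 0.8999 with 10.

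**Step 2: reproduce 166.** 83 / (1 − 0.5) = 166. Conversely, 166 × 0.5 = 83 remain.

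**Step 3: slack.** Power is 0.897 at 82 analysed, 0.890 at 80 and 0.878 at 77. One exclusion takes it below 0.90, and six take it more than two points below.

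**Step 4: assumed exclusion from the 83.** N left = 83 × (1 − e), rounded down; f² = 0.13, p = 1.

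| Assumed share excluded (e) | N left | δ = √(0.13 × N) | Power |
|---|---|---|---|
| 0% | 83 | 3.28 | 0.90 |
| 5% | 78 | 3.18 | 0.88 |
| 10% | 74 | 3.10 | 0.86 |
| 20% | 66 | 2.93 | 0.82 |
| 30% | 58 | 2.75 | 0.77 |

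**Step 5: what lower dropout would absorb.** With 166 enrolled and dropout d, 83 are still analysed if e ≤ 1 − 83 / [166 × (1 − d)].

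- d = 40%: 99.6 complete, so e up to 1 − 83/99.6 = 17%.
- d = 30%: 116.2 complete, so e up to 1 − 83/116.2 = 29%.
- d = 50%: 83 complete, so e = 0.

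**Step 6: the other enrolment figure.** The opening summary table gives a sample size of 120. If that is enrolment, 120 × 0.5 = 60 remain and power is 0.78 before any reporting exclusion.

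**The case against.** The strongest reply is that nothing is miscalculated and the shortfall is conditional. Each part of that reply has some force.

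- **Dropout may be lower.** The 50% is a planning assumption, and phone follow-up is planned to limit loss. Step 5 shows that enrolling 166 then leaves room. This stands, but power quoted for a planned dropout rate should hold at that rate.
- **The 50% may already include unusable diaries.** Non-compliance could be read that way. The documents do not settle it. The text calls the figure a dropout rate during follow-up, and a completed but implausible diary is not plainly dropout. If it was meant to be included, one sentence would say so.
- **The rule may apply only to dietary analyses.** It appears only in the dietary text, so this reading is open, although the text refers to participants. Even then the night-meal model is affected, because its exposure includes the calories of the last meal.

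Two stronger inferences are tempting. A reader might conclude that the study simply does not have its stated power. The documents do not support that unconditionally: dropout must reach the full 50%, the exclusions must be additional to it, and the excluded people must leave the model in question. A reader might also expect a very large loss, because the cut-offs are described as suited to a non-dieting population while routine care recommends reduced calories. That is a reason not to assume the loss is trivial. But the documents give no intake ratios, and the diary instructions tell participants not to change their eating while recording, so no particular rate can be inferred.

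**Conclusion.** The point holds as a gap in planning, not as an error of arithmetic: 83 and 166 both reproduce. The plan has no explicit allowance for the reporting exclusion and no slack to cover it at its own dropout rate. If the exclusions are additional to 50% dropout, any model they leave falls below 90% power, by about 2 points at 5% excluded, 4 at 10%, 8 at 20% and 13 at 30%.

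These sizes rest on assumed exclusion rates, on 166 enrolled, and on f² = 0.13. The last is itself open to question, because the protocol labels 0.13 a β-coefficient. If it is instead a standardised coefficient treated as a partial correlation (an assumption), f² is about 0.017 and power at 83 is about 0.22. That question and the 120 against 166 are separate matters. They do not remove this one, but any restated power must be marked as conditional on both.

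**What to change.** **1. Exposure measures, dietary text.** Limit the exclusion to analyses whose exposure or covariates are computed from diary energy or macronutrients. Keep these participants in models whose exposures come from the CPQ, MCTQ or PSQI, and in all glycemic outcome summaries.

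In the retained models, use the Healthy Eating Index from the food frequency questionnaire as the diet-quality covariate. The Statistical Analysis section elsewhere describes diet quality as the distribution of energy and macronutrients. If that version were set to missing for misreporters, a complete-case model would drop the same people again. The index's scoring formula refers to the diet record, so it should also say that servings are taken from the questionnaire.

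For meal times derived from the diary, report results with and without misreporters, because someone who under-reports may also omit a late meal.

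**2. Sample size Calculation.** State that the 50% does not include the reporting exclusion or, if it was meant to, say so. Restate power for the energy-based models as a range over the number left (for example 0.88 at 78, 0.86 at 74, 0.82 at 66, 0.77 at 58), conditional on the effect size as entered and on enrolling 166. Reconcile the 166 with the 120 in the opening summary table.

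**Cost.** Wording in two places and no extra enrolment. The analysed number will differ between models and must be shown in each table, and the stated power for the energy-based models will be less favourable.

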Study outcomes	
The main outcomes of this study are
 
 1) The change of baseline glycated hemoglobin (HbA1c) among prediabetes adults at 6 months. 2) The change of baseline fasting plasma glucose (FPG) among prediabetes adults at 6 months. 3) The change of baseline 2-hour post-load plasma glucose among prediabetes adults at 6 months. 4) The change of baseline continuous glucose monitoring (CGM) profile among prediabetes adults at 6 months. 
Secondary outcome of this study are
 
 1) The change of eating misalignment among prediabetes adults at 6 months. 2) The change of chronotype among prediabetes adults at 6 months.
Sample Size	120 prediabetic individuals
Study Duration	1 March 2022 until 31 December 2023
Name and Address of Sponsor	Fundamental Research Grant Scheme (FRGS), Ministry of Higher Education/ UMalaya (FRGS/1/2021/SKK06/TARUC/02/1)

Ethics Approval	Tunku Abdul Rahman University Management and Technology Ethics Committee (TAR UC/EC/2021/02-3) Medical Research and Ethics Committee (RSCH ID-21-00114-IVI)
-----------------	---

Executive Summary:

Early meal timing affects the circadian rhythmicity and influenced the postprandial blood glucose level in response to meal in diabetes patients. In the other words, diabetes patients with earlier meal timing had a stable glycemic control compared with those with late meal timing. This is a new concept to switch the meal timing earlier than later in diabetes self-monitoring management. However, there is insufficient evidence from Southeast Asia to determine the optimal-meal-timing and its association with glycemic measures in prediabetes individuals. Hence, this study carried out to determine the associations of chronotype and chrononutrition with glucose tolerance among prediabetic individuals in Malaysia.

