A repeated A1c should be done 4 weeks after the first positive test for asymptomatic patients.

In symptomatic individual, a single positive test is sufficient.

Location of Research:

Location of Research	Expected number of subjects per site
Community Clinic Batu Berendam	56
Community Clinic Bukit Rambai	55
Community Clinic Sungai Udang	55

Recruitment pamphlets that contain general information of the study will be placed in all the healthcare clinics in Malacca. During the process of recruitment, a trained research assistant, clinical dietitian (one of the co-researchers) or family medicine specialist (one of the co-researchers) will inform potential prediabetic individuals of the study both verbally and will be provided written information (Appendix A). Newly diagnosed prediabetic individuals who are agreeable to participate will be provided written informed consent (Appendix A). Study visits (recruitment and follow-up visits) of this study will be determined based on the healthcare clinic appointment schedules. Those who decline to participate continue to receive their routine treatment as usual, and care provided to each prediabetic individual is not affected nor affected by each individual's decision to either participate or not participate in the study. An overview of the study procedure is illustrated in Figure 3. All the newly diagnosed prediabetic individuals who fulfill the inclusion criteria will be invited to participate in the present study. They will be recruited when they visit the diet clinic for the first time for their initial appointment scheduling. This would be considered the baseline visit. OGTT, HbA1c and FBS results will be traced from medical records.

Data regarding sociodemographic information and anthropometric measurements will be collected in the baseline visit. Enrolled participants will be interviewed by a trained

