pattern from the validated questionnaires PSIQ and light exposure from the validated questionnaire HLEQ.

Statistical Analysis

All data will be performed statistical analysis using the SPSS software version 20 (SPSS Inc., Chicago, IL, USA). The socio-demographic will be presented as mean, standard deviations, median, interquartile range, frequency, and percentage. Data cleaning will be performed to exclude the outlier data before the normality is checked using Kolmogorov-Smirnov Test. The investigator considered $p < 0.05$ to be statistically significant. Chronotype, sleep quality, and light exposure will be analyzed as categorical variables whereas dietary intake, chrononutrition, anthropometry, glycemic measure, and physical activity will be analyzed as continuous variables.

The investigator will perform a multivariable generalized linear model to examine the association between night meal pattern (last night mealtime either dinner or supper with calories intake, frequency of night snacking, and the total number of the night snacking) and glycemic outcome (HbA1c, FPG, 2hPPG, CGM profile) by adjusting for the potential covariates. Specifically, nighttime will be characterized by the time range from 1900 and 0659 hours based on Malaysia solar time. The investigator will explore the late-night meal timing in 2000, 2100, and 2200 to examine its association with glycemic outcomes. The potential confounders include sociodemographic characteristics, physical activity, sleep pattern, sedentary behavior, diet quality, and light exposure will be controlled. ANCOVA test will be performed to understand the association between chrononutrition (breakfast skipping, meal frequency, eating window, sleep timing, chronotype, and fasting pattern) with glycemic variables, controlling for potential covariates (sociodemographic characteristics, light exposure, diet quality, physical activity and sleep pattern).

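### The power calculation treats a regression β of 0.13 as f², so 90% power at 83 completers is unsupported for the cited β; the sample size is 120 in the synopsis and 166 elsewhere

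*Combined protocol and SAP*

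**What the plan says.** Under Sample size Calculation (section 3, Research Methodology) the plan uses G*Power with "Statistical Test: Linear Multiple Regression Fixed Model, single regression coefficient", two-sided alpha 0.05 and power 0.90. The input is listed as "Effect Size (β -coefficient): 0.13", and the prose describes it as "the β -coefficient of 0.13 adopted from" a published cohort study of late dinner and glycaemic control in type 2 diabetes. The result is "a total of 83 prediabetic adults expected in this study". Allowing for 50% dropout, 83/(1 − 0.5) = 166, and "total 166 prediabetes individuals shall be recruit in this study".

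The table under Location of Research, in the column "Expected number of subjects per site", lists 56, 55 and 55. The Sample Size row of the synopsis gives "120 prediabetic individuals" and does not say whether these are recruits or completers.

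Under Statistical Analysis, the night-meal model is adjusted for several groups of covariates: "The potential confounders include sociodemographic characteristics, physical activity, sleep pattern, sedentary behavior, diet quality, and light exposure will be controlled".

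**The concern.** A regression coefficient and f² are different quantities. The f² for one coefficient is the variance it explains uniquely, divided by the residual variance. Turning a β into f² requires the standard deviations of predictor and outcome (unless the β is standardised), the residual variance, and the correlation of the predictor with the covariates. The plan gives none of these, and does not say whether the β is standardised.

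This calculation is the only quantitative justification of the study's size, and it concerns the central association, chrononutrition with glycaemic control. If the 90% belongs to a much larger effect than the cited one, a null result could be read as evidence against an association that the study had little chance of detecting. The conflict between 120 and 166 adds doubt about how many completers the study was meant to have.

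**Working it through.** **Method.** Noncentral t for one coefficient in a fixed-model regression: noncentrality δ = √(f² × N), df = N − p − 1 with p predictors, two-sided alpha 0.05.

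**Reproducing the plan's 83.** Take f² = 0.13 and p = 1. At N = 83, δ = √(0.13 × 83) = 3.28 and power is 0.9007. At N = 82 power is 0.8972. So N = 83, as stated. The software output is not shown, so p is unknown, but it hardly matters: N is 83 for 1 to 8 predictors and 84 for 10 to 20.

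**Other readings of 0.13 (p = 1, 90% power).**

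| 0.13 read as | f² | N |
|---|---|---|
| f² | 0.13 | 83 |
| partial R² | 0.13/0.87 = 0.149 | 73 |
| r, or standardised β with no other explained variance | 0.0169/0.9831 = 0.0172 | 614 |
| Cohen's f | 0.13² = 0.0169 | 624 |
| f², one-sided test | 0.13 | 68 |

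Of these, only f² in the stated two-sided test returns 83.

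**What f² = 0.13 means.** Partial R² = 0.13/1.13 = 0.115, and partial |r| = √0.115 = 0.34. For a predictor uncorrelated with the covariates, this equals a standardised β of 0.34 with no other explained variance. It equals √(0.13 × 0.7) = 0.30 at full-model R² 0.3, and √(0.13 × 0.5) = 0.25 at R² 0.5. These are 2.0 to 2.6 times 0.13.

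**Power for the cited β, assuming it is standardised.** Here f² = 0.13²/(VIF × (1 − R²)), where R² is for the full model and VIF is the predictor's variance inflation. Neither is in the plan, so both are assumed ranges. R² = 0.0169 means no other explained variance.

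| VIF | R² | f² | Power at 83 | N for 90% |
|---|---|---|---|---|
| 1 | 0.0169 | 0.0172 | 22% | 614 |
| 1 | 0.3 | 0.0241 | 29% | 438 |
| 1 | 0.5 | 0.0338 | 38% | 313 |
| 1.5 | 0.0169 | 0.0115 | 16% | 919 |
| 1.5 | 0.3 | 0.0161 | 21% | 655 |
| 1.5 | 0.5 | 0.0225 | 27% | 469 |

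Wider assumptions: R² 0.7 with VIF 1 gives 57%, and VIF 2 with no other explained variance gives 13%. With VIF 1, a standardised β of 0.13 reaches f² = 0.13 only if R² = 1 − 0.0169/0.13 = 0.87.

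**If the β is unstandardised.** No f² can be derived, because the plan gives no standard deviations.

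**120 against 166.** The dropout step is right: 83/0.5 = 166 = 56 + 55 + 55. Nothing in the plan produces 120.
- If 120 are recruits, 50% dropout leaves 60 completers, and power is 78% even at f² = 0.13. Keeping 83 completers would require dropout of at most 1 − 83/120 = 30.8%.
- If 120 are completers, power at f² = 0.13 is about 97%, but 120 does not match 83.

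**The case against.** The strongest reply is that the size of the shortfall is unknown. The software output is not shown, so how 0.13 was entered is inferred from the result. The 22% and the 614 depend on a standardised β, which only the cited source could settle, and an unstandardised β could correspond to an f² that is no smaller than 0.13. The R² and VIF limits are the reviewer's: at R² 0.7 power would be 57%. All of this stands as a limit on the size. It does not rescue the 90%, because no reading available in the plan connects that figure to the cited β. If f² was what was meant, the label and the source attribution are wrong.

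On sample size, the methods are internally consistent: 83 completers and 166 recruits, matched by the site targets. That is fair, and it makes 120 an isolated synopsis figure. It is still an unexplained contradiction in a headline row.

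Finally, the study is observational and its visits were scheduled to be over, so the correction changes no estimate or test. That is true, and it is why no extra enrolment is proposed. The stated power will still colour how the results are read.

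**Conclusion.** Both defects hold. The arithmetic behind 83 is correct for f² = 0.13 (partial |r| 0.34), but the plan presents it as power for a β of 0.13 and gives nothing that links the two. The 90% is therefore unsupported for the cited effect. This conclusion needs no assumption about the β. The size of the shortfall does: if the β is standardised, power at 83 completers is about 22% in the simplest case and 16–38% over the assumed ranges, with 313–919 completers needed for 90%. If it is unstandardised, the shortfall cannot be determined from the plan.

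The conflict between 120 and 166 is certain and rests on no assumption. The methods do fix 83 as the number of completers needed, but the synopsis figure agrees with neither 83 nor 166.

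**What to change.** Replace the justification with a statement of this kind:

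> With two-sided alpha 0.05, 83 completers give 90% power for f² = 0.13, that is, partial R² 0.115 or partial |r| 0.34.

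Keep the citation of the β, stop presenting the 90% as power for it, and state whether it is standardised.

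- If it is standardised, add that power at 83 completers is about 22% with no other explained variance and no collinearity, and about 16–38% over full-model R² 0.02–0.5 and VIF 1–1.5. Label these ranges as assumptions.
- If it is not, give the standard deviations and the f² they imply, or say that it cannot be converted.

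Reconcile the synopsis with the Sample size Calculation and the site table to one figure, labelled recruits or completers, with its power at f² = 0.13: 166 recruits and 83 completers, 90%; 120 recruits and 60 completers, 78%; 120 completers, about 97%.

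The cost is protocol wording and a less favourable power statement. The schedule in section 4 ends third visits on 06/03/2024 and the document is dated 6 May 2024, so this corrects the stated justification and does not alter recruitment.
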